#### LIST OF ABBREVIATIONS AND ACRONYMS

AE Adverse Event

CDC Centers for Disease Control and Prevention

CDMS Clinical Data Management System CFR U.S. Code of Federal Regulations

CITI Collaborative Institutional Training Initiative
CLIA Clinical Laboratory Improvement Amendments

eCRF Electronic Case Report Form

FDA U.S. Food and Drug Administration

GCP Good Clinical Practice

HIPAA Health Insurance Portability and Accountability Act

HIV Human Immunodeficiency Virus

ICF Informed Consent Form

ICH International Conference on Harmonization

IRB Institutional Review Board

ISO International Organization for Standardization LGBT Lesbian, Gay, Bisexual, and Transgender

MSA Metropolitan Statistical Area
MSM Men who have sex with men
MSW Men who have sex with women
NIH National Institutes of Health

OHRP Office for Human Research Protections

OSHA Occupational Safety and Health Administration

PrEP Pre-Exposure Prophylaxis

RT-PCR Reverse Transcription-Polymerase Chain Reaction

STI Sexually Transmitted Infection
UNFPA United Nations Population Fund

USAID United States Agency for International Development

#### 1. INTRODUCTION

Male condoms effectively prevent human immunodeficiency virus (HIV) and sexually transmitted infection (STI) transmission, but are underutilized in large part to due to reduced experiences of pleasure. Annually, in the United States, there are approximately 20 million incident cases of STIs, and over 50,000 new HIV infections. The vast majority of new HIV infections (92%) were acquired through vaginal or anal sex, with anal sex alone accounting for more than two-thirds of new infections. The highest priority for any condom promotion effort is to change factors that lead to condom nonuse. Perhaps the most cited and universal reported rationale for not using condoms is the perception that condoms decrease sexual pleasure.

Nearly half of men report poor condom fit; these men are less likely to use condoms. Estimates indicate a range of 35-50% of condom users report poor condom fit. Studies have found that men who have sex with men (MSM) who either perceive condoms as too tight or report larger than average penis size were more likely to report unprotected anal sex. One reason for this is that men who perceive poor condom fit are more likely to report reduced pleasure due to condom use.

The premise of fitted condoms is that better fitting condoms may enhance perceptions of pleasure or overall preference for men considering condom use. We believe that there are two biologically plausible hypotheses for this premise. First, men reporting larger penile size are more likely to describe standard condoms as feeling "tight", 10,12 and this tightness could lead to decreased perceptions of pleasure. Second, men who report smaller penis size are more likely to describe condoms as feeling "loose", 10 and this additional slack (circumference) or rolled (shaft) latex could lead to decreased perceptions of pleasure. There is a scientific need to explore the relationship between fitted condoms and pleasure.

Research is also needed to better understand condom performance for anal sex applications. MSM are estimated to account for nearly two out of every three new HIV infections in the United States,  and are the only group with increasing HIV incidence.  Previous estimates of clinical condom failure (slippage or breakage) during anal sex have often not measured failure at the event level. Two studies have assessed clinical condom failure prospectively at the event level, with clinical failure reported in 6.3%  and 6.9%  of anal sex acts. One study found that fitted condoms had lower breakage failure rates than standard condoms for anal sex. 

For this study, we will use a mobile-optimized, web-based home daily coital log that allows for event level measurement. We anticipate that use of this system will decrease recall bias, avoiding possible limitations of paper-based recall systems that do not have time stamping to accurately determine the time of form completion. We anticipate that, with the use of a system that decreases recall bias, we may have higher sensitivity to detect clinical failure across all study conditions (fitted, thin and standard).

For purposes of this study, a "standard" condom is defined by dimensions commonly sourced by the United Nations Population Fund (UNFPA) and United States Agency for International Development (USAID), which procures the majority of the world's condoms ([name], BS, email communication, June 23, 2015). These dimensions are 185mm ± 10mm length, 53mm

 $\pm$  2mm width, and 70 microns  $\pm$  10 microns thick ([name], BS, email communication, June 23, 2015). "Thin" condoms for this study will be of identical width and length to "standard", but 50 microns  $\pm$  5 microns thick. Fitted condoms will be produced in a range of sizes (uploaded to eIRB) with thickness of 70 microns  $\pm$  10 microns, with a participant's fitted size as determined by their use of a fitting system consisting of a paper template graduated with non-sequential numbering and lettering (uploaded to eIRB). All condoms will be manufactured by Karex International. Condoms will be manufactured using the same latex formulation and silicone lubricants (approximately 400mg per condom), and with similar parallel wall designs.

#### 2. AIMS

The study will enroll 252 MSM and 252 men who sex with women (MSW) into a double-blind, three-way randomized crossover trial with conditions of fitted, thin, and standard condoms. For the MSM arm of the trial we will assess outcomes based on anal sex, and for the MSW we will assess outcomes based on vaginal sex. We are conducting this trial with the objectives of (for Aims 1 and 2) establishing label indications for pleasure and patient preference for fitted condoms, (for Aim 3) establishing a label indication for anal sex for fitted, thin, and standard condoms, and (for Aim 4) establishing a label indication for decreased clinical failure of fitted condoms for anal sex.

**Aim 1.** To compare fitted condoms with standard condoms regarding levels of reported pleasure as determined by rating per condom use event.

**Hypothesis 1.** Fitted condoms will have higher pleasure ratings than standard condoms. **Hypothesis Rationale 1.** There is biological plausibility and published data indicating that condoms fitted to penile dimensions could improve perceptions of pleasure.

**Aim 2.** To compare fitted condoms with standard condoms regarding preference as determined by ranking of the two conditions at the study conclusion.

**Hypothesis 2.** More participants will prefer fitted condoms than standard condoms. **Hypothesis Rationale 2.** There is biological plausibility and published data indicating that condoms fitted to penile dimensions could improve perceptions of pleasure.

**Aim 3.** To assess for fitted, thin, and standard condoms the total clinical failure rate of each type of condom for anal sex among MSM relative to a cut-point to be determined by the United States Food and Drug Administration (FDA).

**Hypothesis 3.** All condom conditions will have clinical failure point estimates less than a cutpoint level of acceptable clinical failure, with the cut-point to be determined by the FDA. **Hypothesis Rationale 3.** Condoms are currently recommended for anal sex use for the prevention of STI and HIV by the U.S. Centers for Disease Control and Prevention (CDC), the United Nations, and the World Health Organization.

**Aim 4.** To compare fitted condoms with standard condoms regarding total clinical failure for anal sex among MSM.

**Hypothesis 4.** Fitted condoms will have a lower total clinical failure rate than standard condoms for anal sex among MSM.

**Hypothesis Rationale 4.** Biological plausibility and published data from a prospective, event-level assessment of clinical failure indicate that fitted condoms may have superior clinical performance for anal sex.

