### 9. STATISTICAL CONSIDERATIONS

### 9.0 Study Aims

The primary aims are:

- 1. To compare fitted condoms with standard condoms regarding levels of reported pleasure as determined by rating per condom use event.
- 2. To compare fitted condoms with standard condoms regarding preference as determined by ranking of the two conditions at the study conclusion.

- 3. To assess for fitted, thin, and standard condoms the total clinical failure rate of each type of condom for anal sex among MSM relative to a cut-point to be determined by the FDA.
- 4. To compare fitted condoms with standard condoms regarding total clinical failure for anal sex.

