ClinicalTrials.gov Study Title: Condom Performance in a Longitudinal Enhanced Assessment of User Experiences (C-PLEASURE)

ClinicalTrials.gov Identifier: NCT02753842

Statistical Analysis Document Date:

Submitted for publication to JMIR – September 13, 2018

Accepted for publication in JMIR – February 14, 2019

Submitted to ClinicalTrials.gov – July 20, 2020

Statistical Analysis

Statistical power and sample size

Using a sample size of $n=504$ randomized participants, assuming 80% retention to $n=403$, and $\alpha=0.05$ we estimated $> 99\%$ power to detect a statistically significant contrast for Aim 1 across a wide range of possible event-level pleasure scores. For Aim 2 at 80% and 90% power, assuming 80% retention, the minimum underlying values of fitted-condom preference $\pi_{2,1}$ that would be detectable as significantly higher than 0.5 ranged from 0.56 to 0.57. Given these calculations, we sought to have at least 404 participants complete the trial. Based on our previous studies in Atlanta, we anticipated 20% loss to follow-up from the 504 enrolled participants.

Data analysis

The planned primary analysis of Aims is described in Table 1.

Table 1. Outcome measures used to assess each study aim

	Aim	Outcome measure
1	To compare fitted condoms with standard condoms regarding levels of reported pleasure as determined by rating per condom use event	Pleasure-scale score (response item mean) for fitted condoms and standard condoms, following each coital event
2	To compare fitted condoms with standard condoms regarding preference as determined by dichotomous preference among the two conditions at the study conclusion	Binary preference of fitted versus standard condoms, at final study visit
3	To assess for fitted, thin, and standard condoms the total clinical failure rate of each type of	Binary occurrence of clinical failure for each type of condom, at each coital event

	condom for anal sex among MSM relative to a cut-point to be determined by the FDA	
4	To compare fitted condoms with standard condoms regarding total clinical failure for anal sex	Binary occurrence of clinical failure for fitted and standard condoms, at each coital event

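### Aims 1, 2 and 4 are three primary superiority tests, each aimed at its own fitted-condom label indication, with no multiplicity control, no stated sidedness and no alpha for Aim 4

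*Protocol*

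**What the plan says.** Protocol section 2 sets the objective for Aims 1 and 2 as "establishing label indications for pleasure and patient preference for fitted condoms". The same paragraph gives Aim 4 a separate objective: a labelled claim that fitted condoms fail less often in anal sex. Section 9.0 introduces Aims 1 to 4 with "The primary aims are" and does not rank them. Hypotheses 1, 2 and 4 (sections 2 and 9.1) all predict that fitted is better than standard. Sections 6.2 and 9.5 say that the results go to FDA.

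Under Statistical power and sample size, the SAP works "assuming 80% retention to $n=403$, and $\alpha=0.05$ we estimated" more than 99% "power to detect a statistically significant contrast for Aim 1 across a wide range of possible event-level pleasure scores". It continues: "For Aim 2 at 80% and 90% power, assuming 80% retention", the smallest values of fitted preference "that would be detectable as significantly higher than 0.5 ranged from 0.56 to 0.57". This paragraph holds the only alpha in the plan. It does not say whether the tests are one- or two-sided, and it gives no alpha or power for Aim 4.

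Under Data analysis, the SAP specifies a linear mixed model (Aim 1), a logistic model (Aim 2) and a logistic mixed model (Aim 4). Neither document gives a testing order, an alpha split, an adjustment or a rule that combines the aims.

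**The concern.** Aims 1, 2 and 4 ask whether the same product beats the same comparator, in the same or overlapping men. Each answer is meant to support its own claim. Section 9.2 gives Aims 1 and 2 an identical rationale, so one premise is tested in two ways. Nothing in the plan requires more than one aim to succeed, or requires one to succeed before another is tested.

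If each test is read at the full nominal level, a fitted condom with no advantage has three chances of a false positive finding. The error rate of the package is then higher than that of any single test. Because the plan omits sidedness and the level for Aim 4, a reader cannot tell how much higher. That matters for a submission whose declared purpose is labelling.

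**Working it through.** **Inputs from the documents**
- 504 randomized and 20% loss: 504 × 0.80 = 403.2, taken as n = 403 (SAP).
- Alpha 0.05, sidedness not stated (SAP).
- Aim 2 detectable preference 0.56 to 0.57 at 80% and 90% power (SAP).
- Three superiority questions, Aims 1, 2 and 4 (protocol sections 2, 9.0 and 9.1).

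**Assumptions (not in the documents)**
- All three null hypotheses are true.
- Aim 4 is tested at the same level as Aims 1 and 2.
- The Aim 1 and Aim 2 test statistics have correlation r, varied from 0 to 0.8. Aim 4 is uncorrelated with both unless stated.

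**Step 1: reproduce the SAP's Aim 2 range to infer sidedness.** For a one-sample proportion against 0.5, by normal approximation:

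p = 0.5 + (z_alpha + z_power) × 0.5/√403, where 0.5/√403 = 0.02491.

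| Alpha | 80% power | 90% power |
|---|---|---|
| One-sided 0.05 | 0.5 + (1.645 + 0.842) × 0.02491 = 0.562 | 0.5 + (1.645 + 1.282) × 0.02491 = 0.573 |
| Two-sided 0.05 | 0.5 + (1.960 + 0.842) × 0.02491 = 0.570 | 0.5 + (1.960 + 1.282) × 0.02491 = 0.581 |

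One-sided 0.05 rounds to 0.56 and 0.57, as printed. Two-sided 0.05 rounds to 0.57 and 0.58, which is not what is printed. Alternative-variance, Wald and exact binomial versions lead to the same conclusion. The Aim 1 power figure cannot be checked, because no difference or standard deviation is given.

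**Step 2: chance of at least one false finding in favour of fitted.** If the tests are independent, this is 1 − (1 − a)³, where a is the error per test in the direction that favours fitted.
- One-sided 0.05 (a = 0.05): 1 − 0.95³ = 14.3%. Upper bound 3 × 0.05 = 15%.
- Two-sided 0.05 (a = 0.025): 1 − 0.975³ = 7.3%. Upper bound 7.5%.

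With correlation, from a trivariate normal distribution:

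| r (Aims 1 and 2) | One-sided 0.05 | Two-sided 0.05, favouring fitted |
|---|---|---|
| 0 | 14.3% | 7.3% |
| 0.3 | 13.8% | 7.1% |
| 0.5 | 13.3% | 6.9% |
| 0.8 | 12.2% | 6.3% |

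If Aim 4 also correlates 0.2 with both other aims, the r = 0.5 row becomes 12.9% and 6.8%.

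**Step 3: fewer true nulls.** If fitted condoms really do give more pleasure, and only Aims 2 and 4 are null and independent, the chance is 1 − 0.95² = 9.75% (one-sided 0.05) or 1 − 0.975² = 4.9% (two-sided 0.05).

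**Step 4: effect of Holm on Aim 2, at one-sided familywise 0.05.** Holm tests the smallest p-value at 0.05/3 = 0.0167, the next at 0.05/2 = 0.025 and the last at 0.05. The formula is that of step 1.

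| Level applied to Aim 2 | 80% power | 90% power |
|---|---|---|
| 0.05 (as now) | 0.562 | 0.573 |
| 0.025 (Aim 1 already rejected) | 0.570 | 0.581 |
| 0.0167 (worst case; z = 2.128) | 0.574 | 0.585 |

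**The case against.** The strongest reply is that the aims seek separate indications for distinct outcomes. The documents never promise a 5% familywise rate, and a sponsor may argue for controlling error claim by claim. That position is open to the sponsor, but the plan neither takes it nor defends it. A fixed sequence or an alpha split would also close the gap, so Holm is one sound choice and not the only one.

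A reader might infer more than the documents support, in three ways.

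- **A flat 13-14% error rate.** This needs one-sided 0.05 for all three tests. That level is stated nowhere and is inferred for Aim 2 alone by back-calculation. Under two-sided 0.05, the 14.3% would count results against fitted condoms as well, and those support no fitted claim. The relevant figure is then about 6-7%.
- **Every test is set at alpha 0.05.** For Aim 4 no level is given. Treating it like the others is an assumption.
- **Any one significant result secures a label claim.** The plan contains no success rule, and for Aims 1 and 2 it describes estimates and confidence intervals. What can be said is that nothing in the plan rules this out.

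The correlations are also assumed. With their shared rationale, Aims 1 and 2 could be strongly correlated, which lowers the figures but does not bring them back to the single-test level.

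It also stands that the correction has a cost, and that this cost must be measured at the sidedness used for the error rate. Imposing two-sided 0.05 on a plan that is really one-sided would tighten sidedness as well as multiplicity.

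**Conclusion.** The point holds in a qualified form. There are three unranked primary superiority tests, each tied to its own fitted-condom label indication, and neither document controls error across them. With all three nulls true, the chance of at least one false finding for fitted condoms is about 12-14% at one-sided 0.05 per test, or about 6-7% at two-sided 0.05. The matching single-test rates are 5% and 2.5%. The first range uses the level that reproduces the SAP's Aim 2 figures. Both ranges assume that Aim 4 is tested at the same level, and that the correlation between Aims 1 and 2 is no higher than about 0.8.

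This should be fixed. It does not invalidate any of the three analyses, and its size depends on a convention that the plan leaves unstated. Aim 3 does not belong in the count, because it compares each condom type's failure proportion with an FDA cut-point and does not test fitted against standard.

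**What to change.** Add to the SAP:
1. The sidedness of the tests for Aims 1, 2 and 4, and one familywise level.
2. A statement that these three aims form one family, tested by Holm at that level and sidedness, and that a fitted-condom label claim needs a Holm-adjusted p-value below it.
3. A statement that Aim 3 is outside this family.

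If the sponsor prefers claim-by-claim error, a fixed order or an alpha split, the SAP should say so and give the reason. Holm has the advantage that no aim has to be ranked first.

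The change is to text and analysis only, but it costs power. At one-sided familywise 0.05 with 403 completers, once Aim 1 has been rejected at the first step, Aim 2's detectable preference rises by 0.008 at either power: 0.562 to 0.570 (80%) and 0.573 to 0.581 (90%). If Aim 2 has to pass at 0.0167, the values are 0.574 and 0.585. The first case is likely if the SAP's power above 99% for Aim 1 also holds at 0.0167. The SAP states that power for alpha 0.05 only. Aim 4 faces a somewhat higher bar too, and since its power is not stated, that loss cannot be sized from the documents.

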#### 3. STUDY OVERVIEW

# 3.0 Study Design

This study is a randomized crossover trial of 252 HIV-negative MSM and 252 HIV-negative MSW. Every participant in the trial will receive a batch of five fitted condoms, a batch of five thin condoms, and a batch of five standard condoms over a series of study visits. We will randomize the order in which fitted, thin, and standard condoms will be distributed. Eventlevel data based on a home coital log will be collected regarding pleasure and total clinical failure (Aims 1, 3 and 4), and data regarding overall condom preference (Aim 2) will be collected at the final study visit. All participants will complete an informed consent form (ICF) (uploaded to eIRB). Eligibility assessment will include HIV testing and symptomatic STI and acute HIV screening. The order in which study condoms will be received will be determined by permuted block randomization. Participants will be provided access to a mobile-optimized, web-based home coital log diary that is 21 U.S. Code of Federal Regulations (CFR) Part 11 compliant, in which participants will document each instance of study condom use as soon as possible following any vaginal or anal sex acts. Log entries will include assessment of pleasure and clinical failure, as well as other pertinent information such as substance use, lubricant, and any potential events including errors during application. Participants will be enrolled over a period of approximately 6-12 months, depending on the speed of recruitment. Each participant will be followed for six to twelve weeks after enrollment, depending on their use of study condoms in each two-week period between study visits (Figure 1). Participants will return for a follow-up visit two weeks after baseline. Participants will be given up to four weeks to use each study condom set; after 4 weeks with a set of condoms, participants will be automatically crossed over into the next study condition. If all condoms are used within the first two weeks, participants will crossover to the next randomized study condoms at that point (Figure 1). If participants do not use all study condoms in the first two weeks after the have been dispensed, participants will be given a second 2-week period to use the batch of condoms. Throughout the duration of study participation, coital logs will be completed.

Figure 1. Visit schedule Baseline Visit Eligible, enrolled participants randomized to CROSSOVER CONDITION 1. Participants will subsequently receive 5 of initial set of condoms (fitted, thin, or control condoms) 2-week visit If all 5 condoms used: CROSSOVER If < 5 condoms used: CONDITION 2 - receive second set additional 2 weeks to use of 5 condoms 4-week visit 4-week visit If all 5 condoms used: CROSSOVER CONDITION 2 -CROSSOVER CONDITION 3 -If < 5 condoms used: additional receive second set of 5 receive third set of 5 condoms 2 weeks to use condoms 6-week visit 6-week visit 6-week visit If all 5 condoms used: If all 5 If <5 condoms used: CROSSOVER CONDITION 3 -If <5 condoms used: CROSSOVER CONDITION 3 condoms additional 2 weeks to receive third set of 5 condoms additional 2 weeks to receive third set of 5 condoms used 8-week visit 8-week visit 8-week visit 8-week visit **END OF STUDY** If <5 condoms used: If all 5 If <5 condoms used: If all 5 CROSSOVER CONDITION 3 additional 2 weeks to condoms additional 2 weeks to condoms receive third set of 5 condoms used used 10-week visit **END OF STUDY** 10-week visit 10-week visit **END OF STUDY END OF STUDY** If all 5 If <5 condoms used: additional 2 weeks to condoms used use **END OF STUDY END OF STUDY END OF STUDY** 12-week visit **END OF STUDY** 

### 3.1 Study Timeline

We estimate the study will start enrolling participants in March 2016, although it may start at an earlier time point. Recruitment will last until 252 eligible MSM and 252 eligible MSW are recruited, approximately 6-12 months. As eligible participants are recruited, they will be scheduled for a baseline screening and enrollment visit. The research team will hold study research events as needed upon study launch. Participants will be able to select a preferred event day and time to complete study visits.

Q4				Q1		Q2		Q3			Q4		Q1					
M	10	M11	M12	M1	M2	M3	M4	M5	M6	M7	M8	M9	M10	M11	M12	M1	M2	M3
	Recruitment						Recruitment and study visits						Enrolled participant study visits, no further recruitment		Results analysis and dissemination			

#### 4. STUDY POPULATION

### 4.0 Sample

Eligible participants will be HIV-negative, aged 18-54 years, live in the Atlanta metro area, and be currently sexually active. We will enroll 252 HIV-negative MSM and 252 HIV-negative MSW. All 504 enrolled participants will be eligible to attend at least four, and up to seven study visits. For purposes of study assignment, men entered into the MSM arm will be defined as a man who intends to only have sex with only other men in the next 12 weeks and men entered into the MSW arm will be defined as a man who intends to only have sex with women in the next 12 weeks. Men who intend to have sex with both men and women in the next 12 weeks will not be included in the sample. Due to potential differences in proficiency with condom use for anal and vaginal sex, anal sex acts reported by men in the MSW arm will be excluded from the analyses.

*Vulnerable populations*: The study will not enroll children, prisoners, pregnant women or any other vulnerable populations.

